4.5 Handling of Missing, Unused and Spurious Data

As a general rule, missing values will not be replaced unless specified otherwise.

5 INTERIM ANALYSIS

An interim analysis will be performed when the last patient has collected last primary endpoint data. An interim clinical trial report will prepared based on data collected up to Visit 9 (Week 24) solely. For each patient, the database cut-off date will be the date of their Visit 9 - Week 24 - Day 4. Further details on the derivation of the interim analysis database can be found in the Data Management Plan.

The following variables are derived only for the interim analysis:

- Completion of treatment phase until Visit 9, reason for premature discontinuation before Visit 9
- Treatment duration until Visit 9: Duration of trial product administration until Visit 9 [days]

Duration of trial product administration until Visit 9 will be calculated as date of last administration until the individual cut-off date – date of first administration +1.

- Study duration until Visit 9: Last visit during treatment phase until Visit 9

 Last visit during treatment phase until Visit 9 will be the last visit of V1 to V9 where a visit date is documented in the eCRF.
- Drug exposure until Visit 9 will be measured by the number of trial product administrations per patient until the individual cut-off date.
- Treatment compliance until Visit 9 will be calculated by dividing the actual number of trial product administrations per patient until the individual cut-off date by the number of trial product administrations theoretically to be applied administered until the individual cut-off date. That means, the actual number of trial product administrations per patient until individual cut-off date will be divided by [1 + the number of weeks until individual cut-off date], whereby number of weeks is the integer part of {[individual cut-off date date of first administration of trial product] / 7}. The result will be multiplied by 100 to obtain a percentage. For patients withdrawn before Visit 9, date of withdrawal will be used instead of individual cut-off date.
- A treatment-boosted ADA positive (until Visit 9) patient (Yes/No) is defined, at the patient level, by an at least 4 fold increase from trial baseline in ADA-titer at any visit until Visit 9 for patients with pre-existing ADA (and a titer at baseline). Thus, it will be missing, if pre-existing ADA is missing or no post-baseline sample is available. It will be "Yes", if the sample at any visit shows a 4 fold increase from baseline and "No" otherwise.
- A treatment-induced ADA positive (until Visit 9) patient (Yes/No) is defined, at the patient level, by a positive ADA sample at any visit until Visit 9 without pre-existing ADA (based on a negative baseline ADA measurement). Thus, it will be missing, if pre-existing ADA is missing or if no post-baseline sample is available. It will be "Yes", if pre-existing ADA is "No" and the sample at any visit is ADA-positive. Otherwise, it will be "No".
- An ADA positive (until Visit 9) patient (Yes/No) is defined by being either treatment-boosted or treatment-induced ADA positive (until Visit 9) (for patients with a baseline ADA measurement). Thus, it will be missing, if pre-existing ADA is missing or if no post-baseline sample is available.
- Overall anti-glepaglutide antibody incidence until Visit 9, i.e. all ADA positive (until Visit 9) patients.

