### 9.4.1 General Considerations

Statistical analyzes will be performed after end of trial, when the database has been locked. The results will be included in the CTR.

The primary analysis will be based on observed data, missing data will not be replaced. Sensitivity analyses with regard to the handling of missing data may be described in the SAP.

In general, data will be summarized using descriptive statistics: Continuous data will be summarized by presenting the number of non-missing observations, mean, standard deviation (SD), median, minimum, and maximum. Categorical data will be summarized by presenting the number of patients and percentage for each category. Listings of individual patient data will be presented.

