3 STATISTICAL ANALYSIS SETS

The analysis of efficacy will be performed based on the Full Analysis Set (FAS, primary statistical analysis) and based on the Per-protocol set (PPS, supportive analysis). The analysis of safety will also be done based on the FAS if this is equal to the Safety Analysis Set (SAS), and based on the Safety Analysis Set otherwise. Allocation of patients to analysis sets will be done prior to data base lock.

Patients who cannot be included in any of the analysis sets mentioned below will be excluded from the statistical analysis, relevant data of these patients will be listed.

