3.2 Per-protocol Set

The PPS comprises all FAS patients without major protocol deviations.

Major protocol deviations may include:

- Violation of one or more relevant inclusion/exclusion criteria
- Absence of on-treatment data
- Insufficient compliance with administration of trial product
- Use of prohibited concomitant therapy
- Insufficient compliance with other procedures/instructions like
 - Deviation from fixed drinking menu / PS volume / Urine volume collection
 - Deviation concerning collection of urine/feces:

An answer of "No" to one or more of the following questions in the eCRF

- Fasting requirement (PS allowed) (Day 2)
- Urinate / defecate / empty stoma bag prior to MBS collection start (Day 2)
- Collection of duplicate food and liquids (Day 2/3/4)
- Urinate / defecate / empty stoma bag end of study (Day 4)
- Other relevant protocol deviations.

The final allocation to and exclusion from the PPS will be made prior to database lock and will be approved by the sponsor. The PPS will be used for supplementary analyses of the primary and key secondary efficacy endpoints.

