2-1	Primary endpoint and key secondary endpoint	ENR	Visit; Analysis Visit; Absorption of wet weight/fluids; Change from baseline to Week 24 in absorption of wet weight/fluids; Absorption of energy; Change from baseline to week 24 in absorption of energy				
2-2.1	Absorption of wet weight/fluids by visit (eCRF)	ENR	Visit; Wet weight intake (oral solid food and oral fluid); Wet weight output (urine and feces); (Metabolic Balance Study Efficacy Data (24Hr) form)				
2-2.2	Absorption of energy by visit (eCRF)	ENR	Visit; Energy Metabolism: energy intake; Energy Metabolism: energy output; (Metabolic Balance Study Efficacy Data (24Hr) form)				
2-3.1	Absorption of individual macronutrients by visit	ENR	Visit; Analysis Visit; Absorption of individual macronutrients: Macronutrient [g/d]; Change from baseline in Absorption of individual macronutrients: Macronutrient [g/d]; Note: Macronutrient is one of Carbohydrate, Lipids, Proteins				
2-3.2	Absorption of individual macronutrients by visit (eCRF)	ENR	Visit; Macronutrients: Macronutrient [g/d] intake; Macronutrients: Macronutrient [g/d] fecal output; Note: Macronutrient is one of Carbohydrate, Lipids, Proteins (Metabolic Balance Study Efficacy Data (24Hr) form)				
2-4.1	Absorption of electrolytes by visit	ENR	Visit; Analysis Visit; Absorption of individual Electrolytes: Electrolyte [g/d]; Change from baseline in Absorption of individual Electrolytes: Electrolyte [g/d]; Note: Electrolyte is one of Sodium, Potassium, Calcium, Magnesium				

2-4.2	Absorption of electrolytes by visit (eCRF)	ENR	Visit; Electrolytes: Electrolyte [mmol/d] intake; Electrolytes: Electrolyte [mmol/d] output;
			Note: Electrolyte is one of Sodium, Potassium, Calcium, Magnesium (Metabolic Balance Study Efficacy Data (24Hr) form)
2-5.1	Metabolic Balance Study Day 1 (Formal Fields)	ENR	Metabolic Balance Study Day 1 form
2-5.2	Metabolic Balance Study Day 2 (Formal Fields)	ENR	Metabolic Balance Study Day 2 form
2-5.3	Metabolic Balance Study Day 3 (Formal Fields)	ENR	Metabolic Balance Study Day 3 form
2-5.4	Metabolic Balance Study Day 4 (Formal Fields)	ENR	Metabolic Balance Study Day 4 form
2-6	Registration of drinking and urine volumes	ENR	Registration of drinking and urine volumes form
2-7.1	Diary Parenteral Support Use	ENR	Diary Parenteral Support Use/Volume form and Diary PS use form

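### As written, per-protocol membership for the Week 24 endpoints can be settled after the interim has shown each patient's Week 24 change, and no cut-off date limits which deviations count

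*SAP*

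**What the plan says.** **When membership is fixed.** SAP 3: "Allocation of patients to analysis sets will be done prior to data base lock". SAP 3.2: "The final allocation to and exclusion from the PPS will be made prior to database lock and will be approved by the sponsor". Protocol Table 10 has the same timing. Protocol 9.4.1: "Statistical analyzes will be performed after end of trial, when the database has been locked". Protocol 4.4 defines end of trial as the last patient's follow-up visit, which is scheduled for Week 56.

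**The interim.** SAP 5: "An interim analysis will be performed when the last patient has collected last primary endpoint data". Each patient's data are cut at Visit 9 Day 4, and an interim trial report is written. On the interim database SAP 5 adds: "Further details on the derivation of the interim analysis database can be found in the Data Management Plan".

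**What the interim shows.** Appendix D removes all PPS tables, the PPS exclusion reasons (Table 1-1.2), the protocol-violation tables and deviation Listings 1-6.1 and 1-6.2. It does not remove Listing 2-1 ("Primary endpoint and key secondary endpoint") or subject-profile Figures 2-1 and 2-2. It also leaves in Table 1-1.1 (counts per analysis set) and Listing 1-1 (analysis-set flags and exclusions).

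**What counts as a deviation.** Protocol Table 10 says that the SAP will list the PPS exclusion criteria. SAP 3.2 opens its list with "Major protocol deviations may include" and closes it with a catch-all item. It gives no compliance threshold and no date limit.

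**Compliance.** SAP 4.2.4 calculates dosing compliance up to the Week 52 (EOT) visit. SAP 5 has a version up to Visit 9, under the introduction "The following variables are derived only for the interim analysis".

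**The concern.** A per-protocol analysis is a useful check only if exclusions are decided without reference to outcomes. Here the order can be reversed: Week 24 changes are reported patient by patient, and the ruling on which deviations are major can follow. The criteria leave room for judgement, and about 8 to 10 patients are planned for analysis, so one reclassification can matter. Energy absorption is more exposed than wet weight because its phase 2 effect size was only 0.28.

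Separately, the PPS definition does not tie deviations to the endpoint. A patient who was fully adherent to Visit 9 could lose a valid Week 24 value because of something that happened later. Conversely, poor adherence before Visit 9 can be diluted by good adherence afterwards.

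**Working it through.** **1. Sequence.** The interim follows the last patient's Week 24 data. The lock follows the last patient's Week 56 visit. Nominal gap: 56 − 24 = 32 weeks. No text in the protocol or SAP requires membership to be final before the interim.

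**2. Which criteria can be met after Visit 9?** Eligibility, the balance-study questions and the fixed drinking menu all end by Visit 9. Dosing compliance, prohibited therapy, PS (parenteral support) volume, urine collection and the catch-all item do not. Of 52 treatment weeks, 52 − 24 = 28 (54%) come after the endpoint.

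**3. The two compliance variables.** Both are doses taken ÷ (1 + whole weeks since first dose). With visits exactly at Weeks 24 and 52, the denominators are 1 + 24 = 25 and 1 + 52 = 53.

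| Patient | To Visit 9 (SAP 5) | To Week 52/EOT (SAP 4.2.4) |
|---|---|---|
| Misses 5 of the first 25 doses, none later | 20/25 = 80% | 48/53 = 91% |
| Takes all doses to Week 32, then stops; EOT visit still at Week 52 | 25/25 = 100% | 33/53 = 62% |
| Same patient, EOT visit held on stopping | 25/25 = 100% | 33/33 = 100% |

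The 91% follows the SAP formula in counting a dose at Week 52; if the last dose falls at Week 51 it is 47/53 = 89%. The 62% requires the EOT visit to stay at Week 52. Protocol 7.1 allows this by encouraging patients who stop treatment to remain in the trial. SAP 4.3.1 points the other way, because it ends treatment-phase data collection on withdrawal from that phase. Listing 1-7 has the dosing-diary entries, so compliance to either date can be derived. The SAP does not say which variable decides PPS membership.

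**4. The plan's own figures.** Effect sizes: 719/340 = 2.11 and 391/1374 = 0.28, as stated in Protocol 9.2. Exact noncentral-t power agrees with Table 9 (for example n=8 at 1.156: 80.0%; n=10 at 1.155: 90.0%). At n=5 and 2.11 it is 93.3% against a stated 90%; n=5 is still the smallest size reaching 90%, since n=4 gives 79.4%.

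**5. Illustration of outcome-aware exclusion.** The documents do not give a number of arguable deviations, so k = 0 to 3 is assumed. Method: 400,000 simulated trials per case, normal changes, one-sample t-test at two-sided 0.05, rejections in favour of benefit. In each trial, k patients have an arguable deviation unrelated to outcome. Any subset of those k may be excluded, including none, and the PPS counts as significant if any choice is.

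| Case | k=0 | k=1 | k=2 | k=3 |
|---|---|---|---|---|
| n=10, no effect | 2.5% | 3.3% | 4.3% | 5.7% |
| n=8, no effect | 2.5% | 3.4% | 4.7% | 6.6% |
| n=10, energy at 0.285 | 12.5% | 14.7% | 17.4% | 20.7% |
| n=10, energy at 0.285, all k excluded by a fixed rule | 12.5% | 11.4% | 10.4% | 9.4% |

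Exclusion by a fixed rule with no true effect stays at 2.5%. For wet weight at 2.11, favourable significance is at least 99.9% whatever is chosen. As an upper bound, if the one or two least favourable of 10 patients were also the ones with excludable deviations, the rate with no true effect would be about 9% or 19%.

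**6. What the excess consists of.** Because excluding nobody is one of the choices, any trial with a significant FAS already counts at k=0. At n=10, k=3 and no effect, 5.7% = 2.5% with FAS significant + 3.2% with PPS alone significant.

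**The case against.** Much of the opposing case stands.

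- **The PPS is only supportive.** A reader might infer that the interim inflates the confirmatory error rate. The documents do not support that: both tests use the FAS, whose membership depends only on having been dosed, and the interim comes after all primary endpoint data are collected.
- **The simulation does not show that agreement between PPS and FAS is weakened.** All the excess is disagreement, with a non-significant FAS that remains the confirmatory result. The model also assumes the number of deviations and a search over every subset.
- **A PPS may already exist at the interim.** Table 1-1.1 and Listing 1-1 stay in, so it would be wrong to infer that no allocation is made by then. No text makes such an allocation final. The Data Management Plan might.
- **The PPS estimand in SAP 4.3.1 points to a limit.** It concerns 24 weeks of treatment, a Week 24 variable and data collected after an intercurrent event; a deviation after Visit 9 does not precede that measurement. This is a reasonable reading, but the limit is not stated. Appendix A also uses the same PPS for Week 52 tables such as 2-3.14, where later deviations are relevant.
- **Results may be known anyway.** The trial is open-label (Protocol 6.3), and entered data are available to the sponsor (Protocol 10.1.8.1). The interim is not the only route to that knowledge.

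Nor do the documents suggest an intention to select patients; the point concerns what the wording permits.

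**Conclusion.** The point holds as a minor one. On the protocol and SAP alone, PPS membership for the Week 24 primary and key secondary endpoints may become final after patient-level changes have been reported, and a deviation after Visit 9 may count against a Week 24 value. The consequence is confined to the credibility of the supportive PPS result, mainly for energy absorption; the wet weight conclusion is robust if the phase 2 effect size holds.

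The simulated rates show the scale of what outcome-aware choice could do; they do not predict what will happen here. The 80% against 91% contrast shows that the two compliance variables can differ materially, while the 62% figure depends on when the EOT visit is held. The timing conclusion would fall away if the Data Management Plan already fixes membership before the interim.

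**What to change.** In SAP 3.2:

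- State that for the Week 24 primary and key secondary endpoints, only deviations up to each patient's Visit 9 Day 4 count towards PPS exclusion.
- State that this membership is documented and signed off before the interim data are analysed, or cite the Data Management Plan if it already requires this.
- Derive compliance until Visit 9 for the final analysis as well, and use it for this Week 24 PPS against a threshold stated in advance.
- Keep a separate PPS flag for the Week 52 tables in Appendix A.

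The cost is one earlier deviation review, cleaning of the Visit 1 to Visit 9 data before it, and a second PPS flag. No new data are needed. In an open-label trial, early sign-off reduces prior knowledge of individual results but does not remove it.

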6 CHANGES FROM PROTOCOL

The analyses planned in this analysis plan deviate in the following point from the provisions in the clinical trial protocol:

- Concerning 8.2.20 Weekly days on PS (SBS-IF only):
 - Weekly average administration time will not be analyzed as it was decided not to collect information on duration of PS use in the patient diary (change from clinical trial protocol version 1.0 to version 2.0).
- Concerning exploratory endpoint "Pharmacokinetic (PK) parameters (t½ and C_{trough})":
 - The parameter $t_{1/2}$ will not be analyzed as it cannot be calculated based on the samples taken (the dosing time prior to Visit 9 may vary between patients).

No relevant deviations from the statistical methods foreseen in the clinical trial protocol are planned.

7 SUMMARY TABLES AND DATA LISTINGS

7.1 Summary Tables

The summary tables planned for this analysis are listed in Appendix A.

The treatment group will be labelled as Glepaglutide – Once Weekly.

General format for categorical variables (SAS output):

		Type of SBS					
Glepaglutide – Once Weekly		SBS-IF		SBS-II		Total	
		N	%	N	%	N	%
Analysis X-Variable Visit							
Week x	Category 1						
	Category 2						
	Number of patients						
Week y	X-Variable						
	Category 1						
	Category 2						
	Number of patients						

More than one X-variable may be analyzed within a table. Variables can have more than two categories. Percentages are displayed with 1 decimal.

General format for continuous variables (SAS output):

Glepaglutide – Once Weekly		X-variable								
		Valid n	Mean	Std. Dev.	Min.	Q25%	Median	Q75%	Max.	Missing n
Type of SBS	Analysis Visit									
SBS-IF	Week x									
	Week y									
SBS-II	Week x									
	Week y									
Total	Week x									
	Week y									

More than one x-variable may be analyzed within a table.

The number of decimals used for minima and maxima depends on the scaling of the respective data. Mean, median and percentiles will be displayed with one additional decimal. Standard deviations will be displayed with two additional decimals. Frequencies (valid n and missing n) will be displayed with no decimals.

7.2 Data Listings

The data listings planned are listed in Appendix B.

Data of all patients screened will be listed. Flags will be provided in the listings indicating which patients are included in the different analysis sets. Patients will be sorted by the screening number and by whether they have SBS-II or SBS-IF.

7.3 Figures

The figures planned are listed in Appendix C.

7.4 Modifications of Summary Tables and Data Listings for Interim Analysis

Modifications of summary tables and data listings are listed in Appendix D.

9 APPENDICES

- A List of Summary Tables
- B List of Data Listings
- C List of Figures
- D Modifications of Summary Tables and Data Listings for Interim Analysis

List of Summary Tables

Analysis Sets:

ALL = All Patients Included into the Trial

FAS = Full Analysis Set

PPS = Per-Protocol Set

SAS = Safety Analysis Set (Note: if FAS=SAS, then FAS will be used)

No.	Title/Content	Analysis Sets				
1. Study Pati	1. Study Patients					
1-1.1	Number of patients screened and included in each analysis set	ALL				
1-1.2	Reasons for exclusion from per-protocol analysis set	FAS				
1-1.3	Study completion: Completion of treatment phase and reasons for premature discontinuation	FAS				
1-1.4	Treatment duration: Duration of trial product administration during treatment phase	FAS				
1-1.5.1	Study duration: Last visit during treatment phase	FAS				
1-1.5.2	Study duration: Follow-up visit performed	FAS				
1-2.1	Inclusion criteria	FAS				
1-2.2	Exclusion criteria	FAS				
1-2.3.1	Protocol violations - Overview	FAS				
1-2.3.2	Protocol violations - Details	FAS				
1-2.4	Compliance with time window for Week 52 (EOT) for completers	FAS				
1-3.1	Demographic data: Sex, age, race, ethnicity, body height and weight	FAS / PPS				
1-3.2.1	SBS characteristics and history: Type, cause and severity of SBS, time since diagnosis of underlying disease, time since SBS diagnosis	FAS / PPS				
1-3.2.2	SBS characteristics and history: Time since most recent resection, reason for resection	FAS / PPS				
1-3.2.3	SBS characteristics and history - Remaining bowel sections - Colon-in-continuity (including type) - End-jejunostomy/SBS anatomical group 1 - Ileostomy/SBS anatomical group 1 - Colostomy - Presence of ileocecal valve	FAS				

No.	Title/Content	Analysis Sets
1-3.2.4	SBS characteristics and history - Bowel lengths - Length of the remnant small bowel - Remnant colon in percent	FAS
1-3.2.5	SBS characteristics and history: Time since start of PS (if applicable)	FAS
1-3.3	Medical history/concomitant illness - Encephalopathy - Ascites - Cholestasis - Steatosis - Cirrhosis	FAS
1-3.4	Baseline characteristics: Substance abuse - Alcohol abuse - Drug abuse - Tobacco smoking	FAS
1-4	Drug exposure and treatment compliance	FAS / PPS
1-5.1	Pre-treatment therapies	FAS
1-5.2	Concomitant therapies commenced or ongoing at date of first administration of trial product	FAS
1-5.3	Concomitant therapies commenced after date of first administration of trial product	FAS

No.	Title/Content	Analysis Sets	
2. Efficacy Ev	2. Efficacy Evaluation and Other Variables		
2-1.1	Primary Endpoint: Change from baseline to Week 24 in absorption of wet weight/fluids	FAS / PPS	
2-1.2	Absorption of wet weight/fluids by visit	FAS / PPS	
2-2.1.1	Key secondary endpoint: Change from baseline to week 24 in absorption of energy	FAS / PPS	
2-2.1.2	Absorption of energy by visit	FAS / PPS	
2-2.2.1.1- 2-2.2.1.3	Absorption of individual macronutrients: Change from baseline to Week 24 - Carbohydrates [g/d] - Lipids [g/d] - Proteins [g/d]	FAS / PPS	
2-2.2.2.1- 2-2.2.2.3	Absorption of individual macronutrients by visit - Carbohydrates [g/d] - Lipids [g/d] - Proteins [g/d]	FAS / PPS	
2-2.3.1.1- 2-2.3.1.4	Absorption of electrolytes: Change from baseline to Week 24 - Sodium [mmol/d] - Potassium [mmol/d] - Calcium [mmol/d] - Magnesium [mmol/d]	FAS / PPS	
2-2.3.2.1- 2-2.3.2.4	Absorption of electrolytes by visit - Sodium [mmol/d] - Potassium [mmol/d] - Calcium [mmol/d] - Magnesium [mmol/d]	FAS / PPS	
2-2.4.1	Weekly parenteral support volume: Change from baseline to Week 12 and 24 (SBS-IF only)	FAS / PPS	
2-2.4.2	Weekly parenteral support volume by visit (SBS-IF only)	FAS / PPS	

No.	Title/Content	Analysis Sets
2-2.5.1.1- 2-2.5.1.7	Weekly parenteral support macronutrients and electrolytes (SBS-IF only): Change from baseline to Week 12 and 24 - Macronutrient: Carbohydrates [kjoule] - Macronutrient: Lipids [kjoule] - Macronutrient: Proteins [kjoule] - Macronutrient: Total content [kjoule] - Electrolyte: Sodium [mmol] - Electrolyte: Potassium [mmol] - Electrolyte: Magnesium [mmol]	FAS / PPS
2-2.5.2.1- 2-2.5.2.7	Weekly parenteral support macronutrients and electrolytes (SBS-IF only) by visit - Macronutrient: Carbohydrates [kjoule] - Macronutrient: Lipids [kjoule] - Macronutrient: Proteins [kjoule] - Macronutrient: Total content [kjoule] - Electrolyte: Sodium [mmol] - Electrolyte: Potassium [mmol] - Electrolyte: Magnesium [mmol]	FAS / PPS
2-3.1.1	Body weight [kg]: Change from baseline to Week 12, 24 and 52	FAS
2-3.1.2	Body weight [kg] by visit	FAS
2-3.2.1.1- 2-3.2.1.3	Body composition by dual-energy X-ray absorptiometry (DEXA): Change from baseline to Week 12, 24 and 52 - Lean body mass [kg] - Fat mass [kg] - Bone mineral content [kg]	FAS
2-3.2.2.1- 2-3.2.2.3	Body composition by dual-energy X-ray absorptiometry (DEXA) by visit - Lean body mass [kg] - Fat mass [kg] - Bone mineral content [kg]	FAS
2-3.3.1	Citrulline: Change from baseline to Week 12, 24 and 52	FAS
2-3.3.2	Citrulline by visit	FAS
2-3.4.1	Aldosterone: Change from baseline to Week 12, 24 and 52	FAS
2-3.4.2	Aldosterone by visit	FAS
2-3.5.1.1	Estimated glomerular filtration rate (eGFR): Change from baseline to Week 12, 24, and 52	FAS

No.	Title/Content	Analysis Sets
2-3.5.1.2	Estimated glomerular filtration rate (eGFR) by visit	FAS
2-3.5.2.1	Creatinine clearance: Change from baseline to Week 12, 24, and 52	FAS
2-3.5.2.2	Creatinine clearance by visit	FAS
2-3.5.3.1.1- 2-3.5.3.1.5	Liver function: Change from baseline to Week 12, 24, and 52 - ALT - AST - ALP - Albumin - Total bilirubin	FAS
2-3.5.3.2.1- 2-3.5.3.2.5	Liver function by visit - ALT - AST - ALP - Albumin - Bilirubin	FAS
2-3.6.1	Hemoglobin A1c: Change from baseline to Week 4, 12, 24 and 52	FAS
2-3.6.2	Hemoglobin A1c by visit	FAS
2-3.7	Patient reported outcome: Patient's global impression of change (PGIC) at Week 12, 24 and 52	FAS
2-3.8.1.1.1- 2-3.8.1.1.8	Patient reported outcome: SBS -impact scale (SBS-I): Change from baseline to Week 12, 24 and 52: - Item 1 - Item 2 - Item 3 - Item 4 - Item 5 - Item 6 - Item 7 - Item 8	FAS

No.	Title/Content	Analysis Sets
2-3.8.1.2.1- 2-3.8.1.2.8	Patient reported outcome: SBS -impact scale (SBS-I) by visit: - Item 1 - Item 2 - Item 3 - Item 4 - Item 5 - Item 6 - Item 7 - Item 8	FAS
2-3.8.2.1.1- 2-3.8.2.1.5	Patient reported outcome: EQ-5D-5L Domains: Change from baseline to Week 12, 24 and 52: - Mobility - Self-care - Usual activities - Pain/discomfort - Anxiety/depression	FAS
2-3.8.2.2.1- 2-3.8.2.2.5	Patient reported outcome: EQ-5D-5L Domains by visit: - Mobility - Self-care - Usual activities - Pain/discomfort - Anxiety/depression	FAS
2-3.8.3.1	Patient reported outcome: EQ-5D-5L Current Health Visual Analogue Scale: Change from baseline to Week 12, 24 and 52	FAS
2-3.8.3.2	Patient reported outcome: EQ-5D-5L Current Health Visual Analogue Scale by visit	FAS
2-3.8.4.1	Patient reported outcome: EQ-5D-5L Index: Change from baseline to Week 12, 24 and 52	FAS
2-3.8.4.2	Patient reported outcome: EQ-5D-5L Index by visit	FAS
2-3.9.1- 2-3.9.4	Pharmacokinetic Analysis: Trough concentrations by visit - Parent drug - Metabolite M1 - Metabolite M2 - Glepaglutide	FAS
2-3.10.1	Luminal- and mucosae-associated microbiota of patients with SBS: Change from baseline to Week 24	FAS

No.	Title/Content	Analysis Sets
2-3.10.2	Luminal- and mucosae-associated microbiota of patients with SBS by visit	FAS
2-3.11.1.1.1- 2-3.11.1.1.4	Urinary excretion of electrolytes: Change from baseline to Week 24 - Sodium [mmol/d] - Potassium [mmol/d] - Calcium [mmol/d] - Magnesium [mmol/d]	FAS / PPS
2-3.11.1.2.1- 2-3.11.1.2.4	Urinary excretion of electrolytes by visit - Sodium [mmol/d] - Potassium [mmol/d] - Calcium [mmol/d] - Magnesium [mmol/d]	FAS / PPS
2-3.11.2.1	Urinary excretion of urea [mmol/d]: Change from baseline to Week 24	FAS / PPS
2-3.11.2.2	Urinary excretion of urea [mmol/d] by visit	FAS / PPS
2-3.12.1	Fluid composite effect [L/d]: Change from baseline to Week 12, 24 and 52	FAS / PPS
2-3.12.2	Fluid composite effect [L/d] by visit	FAS / PPS
2-3.13.1	Drinking volume during 48-hour periods: Change from Week 24 to 52	FAS / PPS
2-3.13.2	Drinking volume during 48-hour periods by visit	FAS / PPS
2-3.14	Weekly parenteral support volume: Change from baseline to Week 52 (SBS-IF only)	FAS / PPS
2-3.15.1- 2-3.15.7	Weekly parenteral support macronutrients and electrolytes (SBS-IF only): Change from baseline to Week 52 - Macronutrient: Carbohydrates [kjoule] - Macronutrient: Lipids [kjoule] - Macronutrient: Proteins [kjoule] - Macronutrient: Total content [kjoule] - Electrolyte: Sodium [mmol] - Electrolyte: Potassium [mmol] - Electrolyte: Magnesium [mmol]	FAS / PPS
2-3.16.1	Weekly days on PS: Change from baseline to Week 12, 24, and 52 (SBS-IF only)	FAS / PPS
2-3.16.2	Weekly days on PS by visit (SBS-IF only)	FAS / PPS

No.	Title/Content	Analysis Sets
2-3.17.1	Urine output: Change from baseline to Week 12, 24 and 52 (SBS-II only)	FAS / PPS
2-3.17.2	Urine output by visit (SBS-II only)	FAS / PPS

No.	Title/Content	Analysis Sets
3. Safety Ev	valuation	
3-1.1	Number of patients with different adverse event categories, overview	SAS
3-1.2	Treatment-emergent adverse events by MedDRA System Organ Class (SOC) and Preferred Term (PT)	SAS
3-1.3	Treatment-emergent adverse drug reactions by MedDRA System Organ Class (SOC) and Preferred Term (PT)	SAS
3-1.4	Treatment-emergent serious adverse events by MedDRA System Organ Class (SOC) and Preferred Term (PT)	SAS
3-1.5	Adverse events leading to permanent discontinuation of study treatment by System Organ Class (SOC) and Preferred Term (PT)	SAS
3-1.6	Treatment-emergent adverse events by severity, seriousness, relationship, action taken with study treatment, and outcome, overview	SAS
3-1.7	Treatment-emergent adverse events by severity and Preferred Term (PT)	SAS
3-1.8	Treatment-emergent adverse events by seriousness and Preferred Term (PT)	SAS
3-1.9	Treatment-emergent adverse events by relationship and Preferred Term (PT)	SAS
3-1.10	Treatment-emergent adverse events by action taken with study treatment and Preferred Term (PT)	SAS
3-1.11	Treatment-emergent adverse events by outcome and Preferred Term (PT)	SAS
3-2.1.1- 3-2.1.4	Vital signs: Change from baseline by visit - Systolic blood pressure - Diastolic blood pressure - Pulse rate - Body temperature	SAS
3-2.2.1- 3-2.2.4	Vital signs by visit - Systolic blood pressure - Diastolic blood pressure - Pulse rate - Body temperature	SAS
3-2.3.1	Body weight: Change from baseline by visit	SAS
3-2.3.2	Body weight by visit	SAS
3-3	Physical examination by visit	SAS

No.	Title/Content	Analysis Sets
3-4.1.1- 3-4.1.6	Electrocardiogram parameters: Absolute changes from baseline by visit - Heart rate [beats/min] - PR [msec] - QRS [msec] - QT [msec] - QTcF [msec] - RR [msec]	SAS
3-4.2.1- 3-4.2.6	Electrocardiogram parameters by visit - Heart rate [beats/min] - PR [msec] - QRS [msec] - QT [msec] - QTcF [msec] - RR[msec]	SAS
3-5.1.1- 3-5.1.10	Laboratory parameters (hematology): Absolute change from baseline by visit - Hemoglobin [mmol/L] - Hematocrit [vol.fr] - Red blood cell count [x10^12/L] - White blood cell count with differential: [x10^9/L] - Neutrophils [x10^9/L] - Lymphocytes [x10^9/L] - Monocytes [x10^9/L] - Eosinophils [x10^9/L] - Basophils [x10^9/L] - Platelet Count [x10^9/L]	SAS
3-5.2.1- 3-5.2.10	Laboratory parameters (hematology) by visit - Hemoglobin [mmol/L] - Hematocrit [vol.fr] - Red blood cell count [x10^12/L] - White blood cell count with differential: [x10^9/L] - Neutrophils [x10^9/L] - Lymphocytes [x10^9/L] - Monocytes [x10^9/L] - Eosinophils [x10^9/L] - Basophils [x10^9/L] - Platelet Count [x10^9/L]	SAS

No.	Title/Content	Analysis Sets
3-5.3.1-	Laboratory parameters (biochemistry): Absolute change	SAS
3-5.3.28	from baseline by visit	
	• Sodium [mmol/L]	
	• Potassium [mmol/L]	
	Chloride [mmol/L]	
	• Bicarbonate [mmol/L]	
	Blood Urea Nitrogen [mmol/L]	
	Creatinine [umol/L]	
	• Creatinine Clearance (estimated) [mL/min]	
	Glucose [mmol/L]	
	• Calcium [mmol/L]	
	• Phosphorous [mmol/L]	
	• ALP (alkaline phosphatase) [U/L]	
	• ALT (alanine aminotransferase) [U/L]	
	• AST (aspartate aminotransferase) [U/L]	
	• INR	
	Gamma-glutamyl transferase (GGT) [U/L]	
	Lactic dehydrogenase [U/L]	
	Conjugated bilirubin [umol/L]	
	Unconjugated bilirubin [umol/L]	
	• Total bilirubin [umol/L]	
	• Total protein [g/L]	
	• Albumin [g/L]	
	• Amylase [U/L]	
	• Uric acid [mmol/L]	
	C-reactive protein [mg/L]	
	• Cholesterol, measured orally fasting [mmol/L]	
	• Triglycerides, measured orally fasting [mmol/L]	
	Magnesium [mmol/L]	
	• Zinc [umol/L]	

No.	Title/Content	Analysis Sets
3-5.4.1-3-5.4.28	Laboratory parameters (biochemistry) by visit Sodium [mmol/L] Potassium [mmol/L] Chloride [mmol/L] Bicarbonate [mmol/L] Blood Urea Nitrogen [mmol/L] Creatinine [umol/L] Creatinine Clearance (estimated) [mL/min] Glucose [mmol/L] Calcium [mmol/L] Phosphorous [mmol/L] ALP (alkaline phosphatase) [U/L] ALT (alanine aminotransferase) [U/L] AST (aspartate aminotransferase) [U/L] INR Gamma-glutamyl transferase (GGT) [U/L] Lactic dehydrogenase [U/L] Conjugated bilirubin [umol/L] Unconjugated bilirubin [umol/L] Total bilirubin [umol/L] Total protein [g/L] Amylase [U/L] Uric acid [mmol/L] C-reactive protein [mg/L] Cholesterol, measured orally fasting [mmol/L] Triglycerides, measured orally fasting [mmol/L] Magnesium [mmol/L] Zinc [umol/L]	SAS
3-5.5.1- 3-5.5.5	Laboratory parameters (urinalysis - by dipstick): Absolute changes from baseline by visit • Blood [x10^6/L] • Glucose [mmol/L] • Leukocytes [x10^6/L] • pH • Protein [g/L]	SAS
3-5.6.1- 3-5.6.5	Laboratory parameters (urinalysis - by dipstick) by visit • Blood [x10^6/L] • Glucose [mmol/L] • Leukocytes [x10^6/L] • pH • Protein [g/L]	SAS

No.	Title/Content	Analysis Sets
3-5.7.1- 3-5.7.6	Laboratory parameters (urinalysis): Absolute changes from baseline by visit - Sodium - Potassium - Calcium - Magnesium - Urea - Creatinine	SAS
3-5.8.1- 3-5.8.6	Laboratory parameters (urinalysis) by visit - Sodium - Potassium - Calcium - Magnesium - Urea - Creatinine	SAS
3-5.9.1- 3-5.9.2	Laboratory parameters aldosterone and citrulline: Absolute changes from baseline by visit	SAS
3-5.10.1- 3-5.10.2	Laboratory parameters aldosterone and citrulline by visit	SAS
3-6.1	Overall anti-glepaglutide antibody incidence Note: Only patients with any evaluable ADA sample	SAS
3-6.2	ADA positive by sample by visit, for patients with/without pre-existing ADA and overall Note: Only patients with any evaluable ADA sample	SAS
3-6.3	Treatment boosted ADA by sample by visit Note: Only patients with pre-existing ADA	SAS
3-6.4	Treatment induced ADA by sample by visit Note: Only patients without pre-existing ADA	SAS
3-6.5.1- 3-6.5.4	Titer levels of treatment induced ADA positive patients by visit - Anti-glepaglutide antibodies (ADA) - Reactivity to M2 - Cross-reactivity to glucagon-like peptide [GLP]-2 - Glepaglutide neutralizing antibodies (NAb) Note: Only treatment induced ADA positive patients	SAS

No.	Title/Content	Analysis Sets
3-6.6.1- 3-6.6.4	Titer levels of treatment boosted ADA positive patients by visit - Anti-glepaglutide antibodies (ADA) - Reactivity to M2 - Cross-reactivity to glucagon-like peptide [GLP]-2 - Glepaglutide neutralizing antibodies (NAb) Note: Only treatment boosted ADA positive patients	SAS
3-6.7.1- 3-6.7.4	Fold increase [%] in titer levels of treatment boosted ADA positive patients from baseline by visit - Anti-glepaglutide antibodies (ADA) - Reactivity to M2 - Cross-reactivity to glucagon-like peptide [GLP]-2 - Glepaglutide neutralizing antibodies (NAb) Note: Only treatment boosted ADA positive patients	SAS

List of Data Listings

Analysis Sets:

ALL = All Patients Included into the Trial

ENR = Enrolled Patients

No.	Title	Set	Variables to be included/Variables of the following form in the eCRF and corresponding derived variables
Patient	Disposition and Baseline Charact	eristics	
1-1	Patient disposition - Allocation to analysis sets, reasons for exclusion from analysis sets	ALL	Date of birth, Screening date; Informed consent date; Rescreenings; FAS, PPS, SAF; exclusion from FAS, PPS, SAF;
1-2	Inclusion and exclusion criteria	ALL	Eligibility check variables (Dosing Criteria – Eligibility and Inclusion/Exclusion Criteria forms)
1-3.1	Study completion	ENR	Completion of treatment phase; Reasons for premature discontinuation (Treatment Completion Status form); Compliance with time window for Week 52 (EOT)
1-3.2	Completion of full study	ENR	Completion of full study; Reason for non-completion (Trial Completion Status form)
1-4.1	Study duration	ENR	Last Visit during treatment phase; Withdrawal Date; Follow-up visit performed
1-4.2	Treatment duration	ENR	First and last trial product administration; Duration of trial product administration; Drug exposure;
1-5	Visit dates	ENR	Visit; Visit Date incl. unscheduled visits and corresponding reason (Date of Visit form)
1-6.1	Protocol deviations - overall	ENR	Data from protocol deviations log

No.	Title	Set	Variables to be included/Variables of the following form in the eCRF and corresponding derived variables
1-6.2	Protocol deviations	ENR	Type of deviation with specification and details; minor or major; reason if minor
1-7	Trial product administration	ENR	Diary Trial Drug Administration form
1-8	Treatment compliance	ENR	All related variables
1-9.1	Demographic data (Part 1)	ENR	Sex, age, race, ethnicity; height, weight; BMI (Demographics and Body Measurements forms)
1-9.2	Demographic data (Part 2)I: Women related information	ENR	Child-bearing potential; Pregnancy Test (Demographics and Pregnancy Test forms)
1-10.1	SBS characteristics and history (Part 1)	ENR	Type, severity and cause of SBS; Time since diagnosis of SBS and of underlying disease; Use of PS at Screening (SBS characteristics and history form)
1-10.2	SBS characteristics and history (Part 2)	ENR	Surgery (including time since most recent resection), remaining bowel sections and bowel lengths (SBS characteristics and history form)
1-11	Medical History/Concomitant Illness	ENR	Any medical condition or event; Medical condition or event; start date; Ongoing at screening; End date; Relatedness to SBS; MedDRA coding (Medical History/Concomitant Illness Header and cont. forms)
1-12	Medical history - SBS	ENR	Encephalopathy, ascites, cholestasis, steatosis and cirrhosis related variables (Medical History – SBS form)
1-13	Substance Abuse	ENR	Substance Abuse form
1-14	Colonoscopy	ENR	Colonoscopy form
1-15	HIV, Hepatitis B and C	ENR	HIV, Hepatitis B and C form
1-16	Drinking Menu	ENR	Drinking Menu and Set Drinking Menu forms

No.	Title	Set	Variables to be included/Variables of the following form in the eCRF and corresponding derived variables
1-17	Physical examination at screening	ENR	Performed; Date; Systems assessed; Evaluation; Clinical Significance (Physical Examination form)
1-18	Parenteral Support Prescription	ENR	Parenteral Support Prescription form
1-19.1	Concomitant medication (Part 1)	ENR	ATC Levels including preferred name and code
1-19.2	Concomitant medication (Part 2)	ENR	CM Number; Indication; Dose (Concomitant Medication form)
1-19.3	Concomitant medication (Part 3)	ENR	Route of Administration; Specification other route of administration; Start and End of drug therapy; Therapy ongoing; Used pre- treatment;(Concomitant Medication Form); Concomitant medicationcategory (pre-treatment, at first dose, after first dose)
1-20	Formal fields (several parts)	ENR	

No.	Title	Set	Variables				
Efficacy	Efficacy Evaluation and Other Variables						
